5.3.2. Reasons for Withdrawal from the Trial

Patients are free to discontinue from the trial at any time without giving any reasons:

5.3.2.1 Patient withdrawal of consent

5.3.2.2 Participation in any other trial during the subject's participation in this trial

In case of withdrawal, patient(s) will be asked to continue safety and survival follow-up every 2 months.

5.3.3. Premature Discontinuation of the Trial

The whole trial may be discontinued prematurely in the event of any of following:

5.3.3.1 New information leading to unfavorable risk benefit judgement of the investigational drug

5.3.3.2 Termination of the clinical trial by the sponsor

5.3.3.3 Evidence of inefficacy

5.3.4. Handling of Participant Withdrawals or Termination

Every effort will be made to keep all randomized patients in the study regardless of their adherence to treatment. Patients who stop their therapy for any reason will be followed until death.

5.4. End of Trial

The definition of end of trial is when the number of events are met for the primary outcome (OS), all available data have been entered into the study database and the study database has been locked. Remaining patients post end of trial, if any, can request Rafael via compassionate use program.

6.1. Description of Study Drugs

6.1.1. Accountability

- The Sponsor (or designee) will ship the study drug product to drug depot. The study drug is accepted by QA and from there it will be supplied to investigational sites. The initial study shipment will be shipped after all the required regulatory documentation has been received and CTA fully executed. Subsequent study drug shipments will be made according to an automated resupply algorithm managed by IxRS.
- The study drug will only be dispensed to patients that meet eligibility criteria and are randomized to a treatment arm in the trials. The number of study drug product vials dispensed will be recorded on an Investigational Product Accountability log. In addition, all doses dispensed should be accounted for by recording the date, study number, patient identification, and balance forward. These records must be maintained and kept at the study site, and will be reviewed by CRO, or its designee, during periodic monitoring visits.
- At the end of the study, any unused drug can be destroyed in compliance with applicable environmental regulations and institution guidelines. Drug destruction must be adequately documented.

[figure not shown]
Procurement of Investigational drugs:

- FOLFIRINOX or modified FOLFIRINOX will not be supplied. They will be obtained from commercially available sources and reimbursed by insurance companies or Rafael Pharmaceutical if it is not offered as a standard of care.

6.1.2. Formulation, Appearance, Packaging, and Labeling

CPI-613[®] (devimistat):

CPI-613[®] (devimistat) is also known as 6,8-bis(benzylthio)-octanoic acid. The chemical name of devimistat is 6,8-bis(benzylsulfanyl) octanoic acid. It is a white to off white crystalline powder with slight sulphurous odor. Its empirical molecular formula is C₂₂H₂₈S₂O₂ and the molecular weight is 388.6 Da. Devimistat has the following chemical structural formula:

Devimistat is freely soluble (~ 140-174 mg/mL) in acetone, chloroform, ethyl acetate, tetrahydrofuran and toluene and insoluble in water (~ 2 mg/mL). The melting point of devimistat is in the range of 65-67°C and predicted pKa value is between 4.9 and 5.4.

Devimistat injection is a sterile, nonpyrogenic, clear, colorless to light yellow solution suitable for intravenous (IV) administration. Devimistat injection is supplied in 10-mL USP type-I amber glass vial with 20 mm grey butyl stopper and royal blue flip off seal. Each mL contains: 50 mg of devimistat and 150 mg of Triethanolamine (TEA). Devimistat injection is a concentrate and must be diluted with 5% dextrose (D5W) injection before use. Devimistat injection is not compatible with saline solution.

FOLFIRINOX:

See locally approved prescribing information for 5-Fluorouracil, folinic acid, oxaliplatin and irinotecan.

6.1.3. Product Storage and Stability

CPI-613[®] (devimistat):

Devimistat injection must be stored in a refrigerator, 2°- 8°C (36° to 46°F) and protected from light. After dilution, the devimistat injection is chemically and physically stable for upto 24 hours at room temperature with normal light exposure. If devimistat injection is to be transferred from one storage area to another, or is to be prepared for dosing, care must be taken to maintain appropriate product temperature. Devimistat injection is slightly photosensitive when exposed to intense light. Therefore, after removal of devimistat drug product from the amber vials, devimistat injection should be administered to patients without unnecessary delay to minimize excessive exposure to light.

FOLFIRINOX (FFX):

All components of FFX including 5-FU, Folinic Acid, oxaliplatin and irinotecan should be handled and stored as per manufactures instructions on the locally approved prescribing information.

6.1.4. Preparation and Handling

CPI-613® (devimistat):

The contents of devimistat injection must be visually inspected prior to dilution to confirm that the contents are clear and colorless to light yellow. If not, it should not be used.

Devimistat is supplied in a 10 mL vial with 500 mg of drug in each vial. Devimistat injection must be diluted from 50 mg/mL to 12.5 mg/mL with 5% dextrose (D5W) prior to administration. The diluted drug product should be visually inspected for clarity. If haziness or precipitate is observed, do not use the diluted drug product for dosing. After dilution with sterile D5W¹⁸, the solution is clear and has a pH of 8.4 - 8.8. The diluted devimistat injection has been found to be stable for 24 hrs. with normal light exposure (please refer to the Pharmacy Manual for study drug dilution and administration guidelines).

D5W will not be supplied.

Handling of CPI-613® (devimistat):

Devimistat is an investigational drug and the toxicity in humans is not fully understood. All necessary precautions in handling potentially toxic chemicals must be strictly adhered to. Gloves and protective clothing must be worn when handling devimistat. Avoid contact by all modes of exposure. If the solution contacts the skin, it must be washed immediately and thoroughly with soap and water. If the solution comes in contact with mucous membranes, the membranes must be flushed thoroughly with water. Spills should be picked up with chemo spill kit. Devimistat drug product is slightly photosensitive. Therefore, after removal of devimistat drug product from the amber vials, devimistat drug product should be protected from excessive light before administration to patients.

Each study site must ensure that the study drug is not used beyond expiry date.

6.1.5. Dosing and Administration

CPI-613[®] (devimistat) and modified FOLFIRINOX (Experimental Arm1: CPI-613[®] (devimistat) + mFFX):

Calculation of the Dose of CPI-613[®] (devimistat) and modified FOLFIRINOX for Each Patient:

The amount of devimistat and each of the drug constituents of modified FFX is based on the body surface area (BSA) of each patient. The BSA values will be calculated based on the height and body weight taken during screening and this BSA value is used throughout the study using a standard formula, such as Mosteller formula. If the subject's body weight changes by >10% from one visit to the next, the BSA should be recalculated and the dose adjusted. There is no maximum dose and patients' actual weight should be used for dose calculation.

The Timing of Dosing (CPI-613[®] (devimistat)):

In a 14-day's cycle (+/- 24 hours), devimistat is to be given on Day 1, prior to administration of mFFX. It is also given on Day 3, after completion of mFFX administration. On day 3, in the event that time will not permit devimistat administration following 5-FU infusion, devimistat may be administered concurrently with 5-FU via a double lumen port.

Administration (CPI-613[®] (devimistat)):

Devimistat must be administered intravenously, via a central venous catheter that is free flowing and free of air in the dead space of the IV catheter, to minimize vascular irritation, inflammation and acute toxicity of devimistat. Accidental co-administration of extra air in the dead space of IV catheters during administration of devimistat has demonstrated the potential to induce acute toxicity of devimistat according to animal studies. Also, accidental leakage of devimistat into the perivascular space during IV administration, which prolongs exposure of perivascular tissue to devimistat, can induce significant local inflammation according to animal studies. To avoid local reactions at and around the site of administration, devimistat must be administered via a central venous catheter.

Diluted devimistat **MUST** be administered as by **IV infusion** and not as bolus via a central venous catheter **at the rate of 4 mL/min** on Day 1 and Day 3 of each cycle via an infusion pump. This is to minimize potential acute toxicity of devimistat, according to animal studies. Devimistat infusion must be administered concurrently with D5W at the rate of 125mL/hour (2.08mL/min) via a central venous catheter.

The following precautions must be taken when administering devimistat:

1. Confirmation of the placement of the IV line to ensure a lack of leakage of devimistat into the perivascular space
2. Confirmation that the IV line is free flowing
3. Confirmation that the IV line is free of dead air space
4. Dilute devimistat drug product with D5W, as instructed in the study protocol
5. Administer devimistat by infusion, not as a bolus
6. After administration of devimistat, flush the IV line with ~10 mL of D5W to remove residual devimistat and to avoid local reactions at and around the site of administration

Intravenous Infusion Sets, Syringes and IV Bags to be Used for Administration of CPI-613[®] (devimistat):

Devimistat must be administered **IV by infusion at the rate of 4 mL/min**, via central venous catheter with D5W running on Day 1 and Day 3 of each cycle. Devimistat infusion must be administered concurrently with D5W at the rate of 125mL/hour (2.08mL/min) via a central venous catheter. To avoid local reactions at and around the site of administration, devimistat should be administered via a central venous catheter. Subsequent sections describe the appropriate types of IV catheters, IV bags, syringes and clinical solutions that can be used in mixing and administering devimistat to patients.

Leaching of Diethylhexyl Phthalate (DEHP) by CPI-613[®] (devimistat):

Devimistat can cause leaching of DEHP from IV infusion sets and IV bags. Therefore, DEHP-containing IV infusion sets, IV bags or syringes SHOULD NOT be used in mixing or administration of devimistat.

Devimistat drug product is slightly photosensitive. Therefore, after removal of devimistat drug product from the amber vials, devimistat drug product should be protected from excessive light before administration to patients.

Disposal of CPI-613[®] (devimistat):

Please refer to the study-specific pharmacy Manual for specific details on the investigational product disposal process. The following procedures are to be taken in disposal of devimistat:

- During the study, store the used devimistat vials (which must be separate from the unused

devimistat vials) at controlled room temperature (20°C-25°C) in an access-limited area.

Alternatively, destroy the used devimistat vials according to institutional guidelines and in compliance with applicable environmental guidelines or return the used and empty vials to the depot. Drug destruction must be adequately documented.

- At the end of the study, deface the label (both used and unused vials) with a permanent marking pen. Destroy used devimistat vials according to institutional guidelines and in compliance with applicable environmental guidelines or return the used and empty vials to depot. Drug destruction must be adequately documented.
- All unused devimistat vials must be returned to the depot

The Timing of Dosing (modified FOLFIRINOX; mFFX):

mFFX is a combination of following 4 drugs:

1. oxaliplatin: day 1
2. folinic acid (calcium folinate or FA): day 1 immediately after oxaliplatin
3. irinotecan: day 1 concurrently with folinic acid
4. flurouracil (5-FU): day 1 bolus followed by a 42-48-hr infusion, starting immediately after completion of folinic acid and irinotecan

Administration (modified FOLFIRINOX; mFFX) (see Table 7 below in detail):

1. oxaliplatin: IV infusion
2. folinic acid (calcium folinate or FA): IV infusion
3. irinotecan: IV infusion
4. flurouracil (5-FU): IV bolus, followed by IV infusion

Maximum Hold Time of modified FOLFIRINOX (mFFX) once Reconstituted before

Administration:

As per the manufacturer's instructions found on locally approved packaging information.

Handling of modified FOLFIRINOX (mFFX):

As per the manufacturer's instructions found on locally approved packaging information.

Disposal of modified FOLFIRINOX (mFFX)

Destroy used vials according to institutional guidelines and in compliance with applicable environmental guidelines. Drug destruction must be adequately documented.

The Table 7 below summarizes the administration of devimistat and mFFX.

Table 7 Administration of CPI-613® (devimistat) and modified FOLFIRINOX (mFFX) in study Arm 1 for Patients with Metastatic Pancreatic Cancer

Treatment Cycle		Administration of CPI-613® (devimistat) and modified FOLFIRINOX (mFFX) in Study Arm 1
Cycle	Day	
Cycle 1	Day 1	
Devimistat: IV infusion at the rate of 4 mL/min at the dose of 500 mg/m² concurrently with D5W at the rate of 125mL/hour (2.08mL/min) via a central venous catheter
 
mFFX (given immediately after devimistat administration):
 
 - Oxaliplatin at 65 mg/m² given as a 2-hr IV infusion - Folinic acid at 400 mg/m² given as a 90-min (1.5 hr) infusion immediately after oxaliplatin, and concurrently with Irinotecan at 140 mg/m² given as a 90-min IV infusion via a Y-connector. - Flurouracil (5-FU) at 400 mg/m² as bolus followed by a 42-48-hr infusion at 2,400 mg/m², starting immediately after completion of folinic acid and irinotecan
	Day 2	
mFFX:
 
 - Completing the remaining of the 5-FU 42-48-hr infusion starting on Day 1
	Day 3	
mFFX:
 
 - Completing the remaining of the 5-FU 42-48-hr infusion starting on Day 1, 2 and disconnect the 5-FU pump. 
devimistat:
 
 - Devimistat (500 mg/m²), IV infusion at the rate of 4 mL/min via a central venous catheter after completion of 5-FU infusion. Devimistat infusion must be administered concurrently with D5W at the rate of 125mL/hour (2.08mL/min) via a central venous catheter. In the event that time will not permit devimistat administration following 5-FU infusion, devimistat may be administered concurrently with 5-FU via a double lumen port.
	Day 4 (-/+ 24 hours)	Myeloid Growth factor per institutional guidelines
	Days 5 -14	No treatment
Cycle 2 and subsequent Cycles (every 2 weeks)		Same as Cycle 1

Dosing as above will continue for at least 6 months in responding patients with acceptable tolerance to therapy (with dose modifications per protocol as needed) unless a criterion for removal from study occurs. Responding patients upon completion of at least 10 cycles and after having two sequential CT scans showing stable disease (no continued decrease in lesion size) will complete 2 additional cycles (to complete a minimum of 12 cycles) of their assigned treatment.

Following 12 cycle and all the subsequent cycles oxaliplatin can be dropped at the discretion of the treating physician if not already omitted. Cycles will continue until one of the criteria for removal from study are reached (Section 5.3.1).

FOLFIRINOX (Control Arm 2; FFX):

Calculation of the Amount of FOLFIRINOX for Each Patient:

The amount of each of the drug constituents of FFX is based on the BSA of each patient.

The BSA values will be calculated based on the height and body weight taken during screening and this BSA value is used throughout the study. The BSA values will be calculated based on a standard formula, such as Mosteller formula. **If the subject's body weight changes by >10% from the dose to the next dose, BSA should be recalculated and the dose adjusted.**

The Timing of Dosing (FFX):

FFX is a combination of following 4 drugs:

1. oxaliplatin: day 1
2. folinic acid (calcium folinate or FA): day 1 immediately after oxaliplatin
3. irinotecan: day 1 concurrently with folinic acid
4. flurouracil (5-FU): day 1 bolus followed by a 42-48-hr infusion, starting immediately after completion of folinic acid and irinotecan

Administration of FOLFIRINOX (FFX) (see Table 8 below in detail):

1. oxaliplatin: IV infusion
2. folinic acid (calcium folinate or FA): IV infusion
3. irinotecan: IV infusion
4. flurouracil (5-FU): IV bolus, followed by IV infusion

Maximum Hold Time of FOLFIRINOX (FFX) once Reconstituted before Administration:

As per the manufacturer’s instructions found on locally approved prescribing information.

Handling of FOLFIRINOX (FFX):

As per the manufacturer’s instructions found on locally approved prescribing information.

Disposal of FOLFIRINOX (FFX)

Destroy used vials according to institutional guidelines and in compliance with applicable environmental guidelines. Drug destruction must be adequately documented.

The Table 8 below summarizes the administration of FFX.

Table 8 Administration of FOLFIRINOX (FFX) in study Arm 2 for Patients with Metastatic Pancreatic Cancer

Treatment Cycle		Administration of FOLFIRINOX (FFX) in study Arm 2
Cycle	Day	
Cycle 1	Day 1	FOLFIRINOX (FFX): - Oxaliplatin at 85 mg/m ² given as a 2-hr IV infusion - Folinic acid at 400 mg/m ² given as a 90-min (1.5 hr) infusion immediately after oxaliplatin, and concurrently with irinotecan (Irinotecan at 180 mg/m ² given as a 90-min IV infusion) via a Y-connector. - Flurouracil (5-FU) at 400 mg/m ² as bolus followed by a 42-48-hr infusion at 2.400 mg/m ² , starting immediately after completion of folinic acid and irinotecan
	Day 2	FOLFIRINOX (FFX): - Completing the remaining of the 5-FU 42-48-hr infusion starting on Day 1
	Day 3	FOLFIRINOX (FFX): - Completing the remaining of the 5-FU 42-48-hr infusion starting on Day 1,2 and disconnect the 5-FU pump.
	Day 4 (+/- 24 hours)	Myeloid Growth factor per institutional guidelines
	Days 5 – 14	No treatment
Cycle 2 and subsequent cycles (every 2 weeks)		Same as Cycle 1

Dosing as above will continue for at least 6 months in responding patients with acceptable tolerance to therapy (with dose modifications per protocol as needed) unless a criterion for

removal from study occurs. Responding patients upon completion of at least 10 cycles and after having two sequential CT scans showing stable disease (no continued decrease in lesion size) will complete 2 additional cycles (to complete a minimum of 12 cycles) of their assigned treatment.

Following 12 cycles, and all the subsequent cycles oxaliplatin can be dropped at the discretion of the treating physician if not already omitted. Cycles will continue until one of the criteria for removal from study are reached (see Section 5.3.1).

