As anticipated, electrolyte imbalance was most frequent and managed with supportive care. No patients died while on active treatment; 11 study participants died, with cause of death as terminal pancreatic cancer.

A total of 20 patients were dosed with devimistat in combination with mFFX and all are included in the safety evaluation. A total of 690 toxicities were reported by the 20 patients, of which 118 were considered Grade 3 or above (17%).

Table 5 Summary of Toxicities in Study CCCWFU57112

CCCWFU57112 (N = 20) - As of April 23, 2019	%*
Grade 3 and Above Toxicities (Treatment Related + Not Related):	17% (118 out of 690 reported toxicities)
Most Frequent Treatment Related** Toxicities (All Grades) Occurring ≥10% of Patients:	
Blood and lymphatic system disorders / Anemia	80%
General disorders and administration sit / Fatigue	75%
Investigations / Platelet count decreased	75%
Gastrointestinal disorders / Diarrhea	70%
Gastrointestinal disorders / Nausea	70%
Metabolism and nutrition disorders / Hyponatremia	70%
Nervous system disorders / Peripheral sensory neuropathy	65%
Investigations / Alkaline phosphatase increased	60%
Investigations / Lymphocyte count decreased	60%
Metabolism and nutrition disorders / Hypokalemia	60%
Investigations / Aspartate aminotransferase increased	55%
Metabolism and nutrition disorders / Anorexia	55%
Investigations / Alanine aminotransferase increased	50%
Metabolism and nutrition disorders / Hypomagnesemia	50%
Nervous system disorders / Dysgeusia	50%
Metabolism and nutrition disorders / Hyperglycemia	45%
Investigations / White blood cell decreased	40%
Metabolism and nutrition disorders / Hypoalbuminemia	40%
Investigations / Neutrophil count decreased	35%
Investigations / Weight loss	35%
Metabolism and nutrition disorders / Dehydration	35%
Metabolism and nutrition disorders / Hypocalcemia	30%
Gastrointestinal disorders / Vomiting	25%
Renal and urinary disorders / Chronic kidney disease	25%
General disorders and administration sit / Pain	20%
Blood and lymphatic system disorders / Leukocytosis	15%

Investigations / Blood bilirubin increased	15%
Metabolism and nutrition disorders / Hypophosphatemia	15%
Gastrointestinal disorders / Mucositis oral	10%
General disorders and administration sit / Edema limbs	10%
General disorders and administration sit / General disorders and administration site conditions – Other	10%
Metabolism and nutrition disorders / Hyponatremia	10%
Metabolism and nutrition disorders / Hypoglycemia	10%

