Nervous system disorders / Dizziness	10%
Psychiatric disorders / Insomnia	10%
Vascular disorders / Thromboembolic event	10%
Grade 5 Toxicities (Treatment Related + Not Related):	0%
Grade 4 Toxicities (Treatment Related + Not Related):	
Blood and lymphatic system disorders / Anemia	5%
Investigations / Platelet count decreased	5%
Investigations / Lymphocyte count decreased	5%
Metabolism and nutrition disorders / Hypokalemia	5%
Metabolism and nutrition disorders / Hyperglycemia	5%
Metabolism and nutrition disorders / Hypoalbuminemia	5%
Investigations / Neutrophil count decreased	5%
Infections and infestations / Sepsis	5%
Grade 3 Toxicities (Treatment Related + Not Related) Occurring ≥10% Patients:	
Metabolism and nutrition disorders / Hyperglycemia	45%
Investigations / Lymphocyte count decreased	30%
Metabolism and nutrition disorders / Hypokalemia	30%
Gastrointestinal disorders / Diarrhea	25%
Metabolism and nutrition disorders / Hyponatremia	25%
Nervous system disorders / Peripheral sensory neuropathy	25%
Vascular disorders / Thromboembolic event	25%
Blood and lymphatic system disorders / Anemia	20%
Investigations / Neutrophil count decreased	20%
Vascular disorders / Hypertension	20%
Gastrointestinal disorders / Abdominal pain	20%
Investigations / Platelet count decreased	15%
General disorders and administration sit / Fatigue	15%
Metabolism and nutrition disorders / Dehydration	15%
Gastrointestinal disorders / Vomiting	15%
Blood and lymphatic system disorders / Leukocytosis	15%
Metabolism and nutrition disorders / Hypophosphatemia	15%

Gastrointestinal disorders / Nausea	10%
Cardiac disorders / Cardiac disorders - Other	10%
Respiratory, thoracic and mediastinal di / Dyspnea	10%
Infections and infestations / Enterocolitis infectious	10%
Infections and infestations / Lung infection	10%
Respiratory, thoracic and mediastinal di / Hypoxia	10%

*% of patients unless otherwise specified; **Adverse events considered by the investigator to be related (probably or possibly related) to study drug treatment in combination [related here refers to combination of both devimistat and mFFX (not devimistat alone)]

Table 6 Clinical Experience of CPI-613[®] (devimistat) in Solid Tumors and Hematological Malignancies

N o.	Trial ID, NCT ID, US FDA IND No.	Phase	Indication	Treatment Detail	#Dosed	#Evaluated for Efficacy	#Evaluated for Safety	Efficacy Summary	Recruitment Status	Result (Interim/Final)	
										Efficacy	Safety

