6.1.6. Dose Adjustments/Modifications/Delays

No dose modifications are allowed for devimistat in this study.

The dose of Folinic Acid is not modified for any toxicity but is omitted if fluorouracil is omitted. Once a dose of any of the drugs comprising FFX is decreased, re-escalation of the dose is not permitted. Patients are taken off the study if they develop the same Grade 4 toxicity despite dose reduction. The dose adjustment scheme for FFX is dependent on the type of toxicities, as described below.

Hematologic Toxicity

Once hematologic toxicity is observed in a patient, do not retreat the patient with mFFX or FFX until the absolute neutrophil count is $\geq 1.5 \times 10^9/L$ and the platelet count is $\geq 75 \times 10^9/L$. The dose modification schemes for FFX related to hematologic toxicity are shown in Table 9.

Primary prophylaxis with myeloid growth factor will be at the discretion of the treating physician and as per the ASCO guidelines. If the patient is not being treated with myeloid growth factor the initial modification for neutropenia should be the addition of a myeloid growth factor. If the patient is already on a myeloid growth factor, then dose adjustments are as outlined in Table 9.

Table 9 Dose Modifications for Hematological Toxicities on Day 1 of a Cycle. Cycles are Every Two Weeks.

Day 1	Delay the Start of a Treatment Cycle*	Doses Reduction		
		Irinotecan	Oxaliplatin	Fluorouracil (5-FU)
ANC <1.5x10 ⁹ /L	Withhold treatment until granulocytes ≥1.5x10 ⁹ /L.	1 st occurrence: Continue same dose	1 st occurrence: Continue same dose	1 st occurrence: Delete bolus 5-FU
		2 nd occurrence: Reduce to 80% of starting dose	2 nd occurrence: Continue same dose	
		3 rd occurrence: Reduce to 50% of starting dose	3 rd occurrence: Reduce to 80% of starting dose	
		4 th occurrence: Discontinue irinotecan	4 th occurrence: Continue on 80% of starting dose	
Platelets <75x10 ⁹ /L	Withhold treatment until platelets ≥75x10 ⁹ /L.	1 st occurrence: No dose reduction	1 st occurrence: No dose reduction	1 st occurrence: Delete bolus 5-FU
		2 nd occurrence: Reduce to 80% of starting dose	2 nd occurrence: Reduce to 80% of starting dose	
		3 rd occurrence: Reduce to 50% of starting dose	3 rd occurrence: Discontinue oxaliplatin	
		4 th occurrence: Discontinue irinotecan	4 th occurrence: Discontinue oxaliplatin	

Table 10 Dose Adjustments According to Non-Hematological Toxicities (Excluding Alopecia, Nausea and Vomiting).

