7.3. Study Schedule

7.3.1. Screening

7.3.1.1 **Screening Visit:** day: -28

7.3.1.2 **Informed Consent:** Obtain informed consent of potential participant verified by signature on written informed consent for screening form

7.3.1.3 **Medical History:** Review medical history to determine eligibility based on inclusion/exclusion criteria

7.3.1.4 **Medical Examinations:** Perform medical examinations needed to determine eligibility based on inclusion/exclusion criteria

Pre-Study Screening Tests & Pre-Study Safety Assessment:

Pre-Study Screening Tests:

Pre-study screening tests, which are also enrollment evaluations, must be performed according the following time frames:

- Within 4 weeks of randomization: tumor assessments (triphase contrast CT of the chest, abdomen and pelvis or MRI), and optional blood and serum samples.
- Within 2 weeks of randomization: medical history, physical exam, vital signs (including heart rate), height, weight, ECG, ECOG, Hemoglobin A1c, evaluation of symptoms and medications, clinical chemistry, hematology, CA19-9 and coagulation.
- Within 1 week of randomization: Serum pregnancy test for women of child-bearing potential.

Pre-Study Safety Assessment:

All safety assessment tests are performed during screening (performed within 2 weeks prior to treatment with devimistat) with results available from local labs for review within 24 hrs. before administration of the anti-tumor agents. These safety assessments include:

- Evaluation of symptoms
- Vital signs including heart rate
- ECOG performance status and survival
- Clinical chemistry
- NCCN-FACT FSHI-18 questionnaire (PRO)
- Renal function
- Hematology
- Coagulation (PT and aPTT)
- CA19-9

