11.2. Institutional Review Board/ Independent Ethics Committee

The protocol, informed consent form(s), recruitment materials, and all participant materials will be submitted to the IRB for review and approval. Approval of both the protocol and the consent form must be obtained before any participant is enrolled. Any amendment to the protocol will require review and approval by the IRB before the changes are implemented to the study. All changes to the consent form will be IRB approved; a determination will be made regarding whether previously consented participants need to be re-consented.

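### In both arms the >10% weight trigger compares consecutive visits or doses, so gradual weight loss never prompts a BSA recalculation, whatever the cumulative loss

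*Protocol*

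**What the plan says.** Section 6.1.5 of the protocol calculates BSA from height and weight at screening, and for Arm 1 adds that "this BSA value is used throughout the study using a standard formula"; Mosteller is the example named. The Arm 1 exception applies when a patient's "body weight changes by >10% from one visit to the next, the BSA should be recalculated and the dose adjusted". A further Arm 1 sentence sets no dose maximum and calls for actual weight in the calculation.

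The Arm 2 text also carries the screening BSA forward. Its exception applies when "body weight changes by >10% from the dose to the next dose, BSA should be recalculated and the dose adjusted".

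Section 6.1.6 states: "No dose modifications are allowed for devimistat in this study". It also bars raising the dose of any FFX drug again once that dose has been decreased.

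On measurement, the screening list in Section 7.3.1 names weight separately from vital signs: "physical exam, vital signs (including heart rate), height, weight, ECG, ECOG, Hemoglobin A1c". Section 5.3 lists weight and BSA at the End of Treatment visit. The cycle-by-cycle lists in Sections 7.3.2 and 7.3.3 and the schedules in Tables 16 and 17 name no on-treatment weight.

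**The concern.** Both exceptions measure change over one interval only. A patient who loses a little each cycle stays under the threshold every time, while the gap between the screening BSA and the true BSA keeps growing. The dose per actual m² then drifts above the protocol dose, and no text in Section 6.1.5 asks the site to correct it. Section 12.3 allows departures from the protocol only for an immediate hazard and permits no waivers. A site that re-doses on cumulative loss therefore has no text to rely on, and practice may vary across about 78 sites.

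Weight loss is foreseeable in this population. In Table 5 (Section 2.1.5.2.1) the item "Investigations / Weight loss" appears among treatment-related toxicities in 35% of the 20 phase I combination patients. The drift matters most for devimistat. Its 500 mg/m² dose was declared the maximum tolerated dose with mFFX, both patients given 1,000 mg/m² had dose-limiting toxicity, and no level in between is reported. Since devimistat dose modification is not allowed, a BSA recalculation is the only way to lower its dose short of delaying or stopping treatment.

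**Working it through.** The plan gives no figure of its own on this point, so the check applies the written rule to stated assumptions.

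**Inputs from the documents**
- BSA = √(height × weight / 3600) (Mosteller; protocol Section 6.1.5 and SAP Section 5.6).
- 14-day cycles, with at least 12 cycles in responding patients (Section 7.3.2).
- Devimistat 500 mg/m².
- Trigger: more than 10% between consecutive visits (Arm 1) or doses (Arm 2).

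**Assumptions**
- Constant height and a steady loss of fraction r per cycle from Cycle 1, with r = 1%, 2% or 3%. The documents give no pace of loss, so this is a range and not an estimate.
- One weighing interval per cycle. Shorter intervals would make the written trigger still harder to reach.

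**Formulas**
- Weight at Cycle k as a fraction of screening weight: (1 − r)^(k−1).
- Excess dose per actual m² under the current rule: (1 − r)^(−(k−1)/2) − 1. Height cancels, so body size does not matter.
- Alternative rule: recalculate when weight differs by more than 10% from the weight behind the current dose, then reset the reference. If weight is checked on the dosing day, the excess cannot exceed 1/√0.90 − 1 = 5.4%.

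**Cycle 12 under the current rule (11 intervals)**
- r = 1%: 0.99^11 = 0.895, loss 10.5%; 1/√0.895 − 1 = 5.7%.
- r = 2%: 0.98^11 = 0.801, loss 19.9%; excess 11.8%.
- r = 3%: 0.97^11 = 0.715, loss 28.5%; excess 18.2%.

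For devimistat these equal about 528, 559 and 591 mg/m² of actual BSA.

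| Loss per cycle | Current rule fires | Excess at Cycle 12 | Mean excess, Cycles 1–12 | Alternative fires at | Largest excess | Mean excess |
|---|---|---|---|---|---|---|
| 1% | never | 5.7% | 2.8% | Cycle 12 | 5.2% | 2.3% |
| 2% | never | 11.8% | 5.8% | Cycle 7 | 5.2% | 2.6% |
| 3% | never | 18.2% | 8.9% | Cycles 5 and 9 | 4.7% | 2.3% |

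Averaged over 12 cycles, the alternative removes 0.5, 3.2 and 6.6 percentage points of excess, or about 2, 16 and 33 mg/m² of devimistat. It changes the dose in 1, 6 and 8 of the 12 cycles.

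**How common and how severe weight loss was in phase I.** 35% of 20 is 7 patients (exact 95% CI 15% to 59%). Weight loss is absent from the Grade 4 list and from the list headed "Grade 3 Toxicities (Treatment Related + Not Related) Occurring ≥10% Patients". Ten per cent of 20 is 2 patients, so at most 1 had Grade 3 loss.

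**The case against.** **Weighing.** A reader might infer that patients are not weighed on treatment. The documents do not support that. The trigger cannot be applied without a weight at each visit or dose, so the rule presupposes one. Tables 16 and 17 are not a full inventory: they show no weight row even at screening and End of Treatment, where Sections 7.3.1 and 5.3 require it. The two End of Treatment lists also disagree, since Section 7.3.4 omits weight. What stands is a secondary gap: the measurement that the dosing rule needs is not listed during treatment. The Pharmacy Manual was not available to check.

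**Actual weight.** The Arm 1 sentence could be read as current weight at every dose. That reading would contradict the carried-forward screening BSA and leave the 10% trigger with nothing to do. Paired with the absence of a maximum dose, the sentence more naturally rules out capping or ideal-weight substitution. Arm 2 has no such sentence.

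**Size.** The 2% and 3% cases need uninterrupted loss of about 20% and 28% over 22 weeks on unchanged treatment. Section 5.3.1 lets the physician stop when the patient's condition changes, and severe loss was rare in phase I. At 1% per cycle the alternative acts only at Cycle 12. This objection stands as a limit on size, but it does not change how the rule works.

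**Harm and bias.** A reader might infer overdosing toxicity or a biased survival comparison. Neither is supported. The documents do not say how phase I updated BSA, so whether the excess is harmful is unknown. The FFX drugs also have toxicity-driven reductions to 80% or 50%, which are larger than the modelled excess. The trigger has the same weakness in both arms.

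**Timing.** SAP Section 5.1.1 plans the analysis on 528 randomized patients, against about 500 in the protocol. This suggests, without proving, that accrual was complete or nearly so. An amendment might then help few patients.

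**Conclusion.** The point holds as a **minor** dosing-consistency and safety point in both arms. On the text, a loss of 10% or less per interval never requires a recalculation, whatever it adds up to. Under the assumed steady losses of 1% to 3% per cycle, the Cycle 12 dose per actual m² is 5.7% to 18.2% too high, against a ceiling of about 5.4% under a rule tied to the current dosing weight. The existence of the gap follows from the wording alone. Its size depends on the assumed loss rates and on treatment continuing without interruption. The finding does not touch the sample size, the type I error or the primary analysis.

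**What to change.** In both arms, replace the trigger with one sentence: recalculate BSA when weight on Day 1 of a cycle differs by more than 10% from the weight used for the current dose, initially the screening weight. State that a BSA-driven change is not a toxicity dose reduction under the no-re-escalation rule of Section 6.1.6; otherwise dosing after weight regain is unclear. Add a Day 1 weight row to Tables 16 and 17.

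The new rule would also raise doses on cumulative weight gain, which was not modelled here.

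In the worked cases the change adds one or two recalculations per affected patient over 12 cycles. The main cost is procedural, because this amends a dosing rule mid-trial: "Any amendment to the protocol will require review and approval by the IRB before the changes are implemented to the study". It also has to be rolled out to about 78 sites, and patients enrolled early and late would be dosed under different triggers, in both arms alike. It can wait for the next amendment, but the benefit shrinks if accrual is nearly complete.
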